8.2 Populations for Analyses

- All Enrolled Subjects: All subjects who signed an informed consent form and were registered into the IVRS.
- All Assigned Subjects: All subjects who were assigned to the highest tested tolerated dose level in the Dose Escalating Safety Evaluation Phase or to any treatment group during the Staged Enrollment Phase.
- All Treated Subjects: All subjects who received at least one dose of any study medication.
- All PK Subjects: All assigned subjects with available serum time-concentration data.
- All Immunogenicity Subjects: All treated subjects with baseline and at least 1 post baseline immunogenicity assessment.
- All Crossover Subjects: All treated subjects who crossed over from Arm N to Arm N-I. SCLC subjects from the expansion cohorts under or after Amendment 09 are excluded from the crossover option.
- All PD-L1 tested subjects: All subjects who had a tumor tissue sample available for assessment of PD-L1 expression at baseline.
- All treated, PD-L1 tested subjects: All PD-L1 tested subjects who received at least one dose of study treatment.
- All PD-L1 evaluable subjects: All treated PD-L1 tested subjects with quantifiable PD-L1 expression.

*Those subjects in the Dose Escalation Safety Evaluation Phase who received at least one dose of the highest dose level confirmed for further investigation will be counted as part of the required 18 treated subjects for Stage 1. In addition to being included in the All Treated Subjects population, those subjects will also be included in the All Dose Escalation Subjects population. Those subjects in the Dose Escalation Safety Evaluation Phase who received at least one dose of a dose level that was not confirmed for further investigation will not be included in the All Treated Subjects population.

8.3 Endpoints

The endpoint definitions apply to all cohorts, unless otherwise specified.

8.3.1 Primary Endpoint(s)

The primary endpoint is the objective response rate (ORR). The ORR is defined as the number of subjects with a best overall response (BOR) of complete response (CR) or partial response (PR) divided by the number of treated subjects. The BOR is defined as the best response designation, as determined by the investigator or BICR for selected tumor types, recorded between the date of randomization or treatment assignment and the date of objectively documented progression per RECIST 1.1 or the date of subsequent anti-cancer therapy, whichever occurs first. CR or PR determinations included in the BOR assessment must be confirmed by a second scan no less than 4 weeks after the criteria for response are first met. For subjects without documented progression or subsequent therapy, all available response designations will contribute to the BOR assessment. For subjects who continue treatment beyond progression, the BOR should be determined based on response designations recorded up to the time of the initial RECIST 1.1-defined progression.

For the SCLC expansion cohort, the estimated difference along with its corresponding p-value of ORR assessed by BICR between nivolumab monotherapy and nivolumab / ipilimumab combination therapy (nivolumab 1 mg/kg + ipilimumab 3 mg/kg) will be provided. In addition, 95% CI (two-sided) will also be presented for the estimated difference of ORR between nivolumab monotherapy and nivolumab / ipilimumab combination therapy.

Similar methods will be used to summarize ORR for each stratification factor (no p-value will be provided).

ORR will be further characterized by the duration of response (DOR) and the magnitude of reduction in tumor volume. DOR will be computed for subjects with a BOR of PR or CR and is defined as the time from first confirmed response (CR or PR) to the date of the first documented tumor progression as determined using RECIST 1.1 criteria or death due to any cause, whichever occurs first. For subjects who neither progress nor die, the DOR will be censored using the same censoring algorithm as used for PFS in Section 8.3.2. The magnitude of reduction in tumor volume is defined as the percent decrease in tumor volume from baseline to nadir, observed up until the time of the first documented tumor progression or death.

These measures of response will be interpreted in the context of historical responses observed following treatment with approved agents.

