^a Subjects received ipilimumab immediately prior to study entry, within 4 - 12 weeks of initiating nivolumab monotherapy on the protocol.

Abbreviations: CI: confidence interval, Ipi: ipilimumab, Nivo: nivolumab, ORR: objective response rate, PFS: progression-free survival

Source: Preliminary data, MDX1106-04. Clinical cut-off date 15-Feb-2013.

After noting that several patients had very deep responses (approaching complete response), a post hoc analysis of the number of patients with tumor reduction of 80% or more was done (Figure 1.1.8.3-1 and Figure 1.1.8.3-2). This depth of response was uncommon in published studies of ipilimumab or nivolumab.^{2,34} A total of 16 out of 52 evaluable patients had tumor reduction of 80% or more at 12 weeks, including 5 with a complete response.

In the combination cohorts, overall evidence of clinical activity (conventional, unconfirmed, or immune-related response or stable disease for ≥ 24 weeks) was observed in 65% of patients (95% CI, 51 to 78). Responses were ongoing in 19 of 21 patients who had a response, with the duration ranging from 6.1 to 72.1 weeks at the time of data analysis.⁸²

Figure 1.1.8.3-1: Study CA209004 Clinical Activity - Tumor Shrinkage over Time

[figure not shown]
[figure not shown]

Figure 1.1.8.3-2: Study CA209004 Clinical Activity - Maximum Tumor Shrinkage

Representative spider plots in [Figure 1.1.8.3-1](#) show changes from baseline in the tumor burden, measured as the sum of the products of perpendicular diameters of all target lesions, in patients who received the concurrent regimen of nivolumab (at a dose of 1 mg per kilogram of body weight) and ipilimumab (3 mg per kilogram), the maximum doses that were associated with an acceptable level of adverse events. Triangles indicate the first occurrence of a new lesion. Dashed lines indicate 50% and 80% improvement from baseline (gray line) in target lesions, as assessed by means of modified World Health Organization criteria. [Figure 1.1.8.3-2](#) shows a representative waterfall plot of the maximum percentage change in target lesions, as compared with baseline measurements, in patients who received the concurrent regimen. A total of 47 patients had a response that could be evaluated in this analysis; 46 had a positive or negative change in target lesions from baseline, and 1 had no change. The dashed line denotes 80% tumor reduction in target lesions from baseline.⁸³

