3.1.2.1 Evaluation of Risk/Benefit for Doses that do not meet Tolerable Criteria

In the event of ≥ 3 of the first 9 subjects requiring permanent discontinuation, a discussion with investigators may be held to review the risk/benefit of this regimen. The rationale for this evaluation is that the most frequent severe drug related AEs for the combination in melanoma have been asymptomatic, reversible laboratory events (ie, LFTs and lipase) and there is preliminary evidence of deep and durable responses in the N-I arm in advanced melanoma (CA209004). Therefore, a discussion of the risk/benefit of the regimen will be triggered if the following criteria are met:

- A majority of subjects who discontinue due to treatment related AEs have deep tumor response (ie, $> 80\%$ reduction)
- All treatment related AEs leading to discontinuation are non-fatal, reversible and without severe sequela (ie, GI perforation)
- A majority of the treatment related AEs are laboratory in nature, asymptomatic, and monitorable via routine blood draws

If a decision is made to continue with a regimen because of a favorable risk/benefit profile (ie, non-fatal AEs in subjects with near CRs that are durable) and despite meeting the ‘not tolerable’ criteria above, then IRBs must be notified, ICFs must be updated, and discussion of the risk/benefit must be documented with all future subjects who enroll on this regimen.

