Procedure	For Arm N-I Dose level 2d, Nivolumab is administered every 2 weeks, Ipilimumab is administered every 6 weeks, cobimetinib is administered orally 21 days on/7 days off	Notes
	Day 1 Week 1, 3, 5, 7, 9, etc	
Clinical Drug Supplies		
IVRS Drug Vial Assignment	X	
Administer Study Treatment	X Nivolumab is administered every 2 weeks, Ipilimumab is administered every 6 weeks, cobimetinib is administered orally at 60 mg (three 20 mg tablets) qd 21 days on/7 days off	See Section 4.5 , Note: Within 3 days from vial allocation, the subject must receive the first dose of study medication. Subjects may be dosed with nivolumab alone or nivolumab and ipilimumab no less than 12 days between doses and no more than 3 days from the scheduled dose. Nivolumab and Ipilimumab both administered as 30-min IV infusion.

Table 5.1-7: Follow-up Assessments (CA209032) - All Subjects			
Procedure	Follow Up,^a Visits 1 and 2	Survival,^b Follow up Visits	Notes
Safety Assessments			
Targeted Physical Examination	X		To assess for potential late emergent study drug related issues
Adverse Event Assessments	X	X	eSAEs should be approved in TAO within 5 days from entry. AEs during the survival follow up visits considered study drug related should be followed until resolution, stabilization, or returned to baseline.
Laboratory Tests	X		CBC w/ differential, LFTs, BUN or serum urea level, creatinine, albumin, Ca, Mg, Na, K, Cl, LDH, glucose, amylase, lipase, TSH (if TSH result abnormal, subsequent testing of Free T4 and Free T3 required).
Pregnancy Test (WOCBP Only)	X		Serum or urine
████████████████████	█		████████████████████
████████████████████			
████████████████████	█		████████████████████
████████████████████			
████████████████████	█	█	████████████████████
Efficacy Assessments			
Tumor Assessments	See Notes		
Only for subjects without progression on study therapy and even if they receive subsequent treatment.
 
Tumor assessments should occur every 6 weeks (\pm 1 wk) from first dose for the first 24 weeks, then every 12 wks (\pm 1 wk) until disease progression or treatment is discontinued, except for subjects who discontinued treatment for other reasons than PD.
 
CT chest, CT or MRI abdomen, pelvis and all known sites of disease. Use same imaging method as was used at screening/baseline.
 
Subjects with a history of brain metastasis should have surveillance MRI approximately every 12 weeks, or sooner if clinically indicated

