2 BASELINE DOCUMENTATION OF 'TARGET' AND 'NON-TARGET' LESIONS

2.1 Target lesions

When more than one measurable lesion is present at baseline all lesions up to **a maximum of five lesions total (and a maximum of two lesions per organ) representative of all involved organs should be identified as target lesions** and will be recorded and measured at baseline.

Target lesions should be selected on the basis of their **size** (lesions with the longest diameter), be representative of all involved organs, and should lend themselves to **reproducible repeated measurements**.

A **sum of the diameters** (longest for non-nodal lesions, short axis for nodal lesions) for all target lesions will be calculated and reported as the **baseline sum diameters**. If lymph nodes are to be included in the sum, then as noted below, only the **short axis** is added into the sum. The baseline sum diameters will be used as reference to further characterize any objective tumor regression in the measurable dimension of the disease.

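### The depth-of-response window in 8.3.1 lacks the cut at subsequent anti-cancer therapy that BOR has, so a nadir from the next treatment can be counted; the measure is also misnamed as volume

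*Protocol*

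**What the plan says.** Section 8.3.1, in the same wording in Revised Protocol 07d and Revised Protocol 08, uses duration of response and depth of response to characterise ORR further. On depth it says: "The magnitude of reduction in tumor volume is defined as the percent decrease in tumor volume from baseline to nadir". The values that count towards this are those "observed up until the time of the first documented tumor progression or death". For best overall response (BOR), the same section closes the window at documented progression "or the date of subsequent anti-cancer therapy, whichever occurs first". Section 5.4.2 also stops BOR at subsequent therapy.

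Section 8.3.2 censors PFS at the last evaluable assessment before new anti-cancer therapy. DOR borrows that censoring rule for subjects who neither progress nor die.

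On imaging after treatment stops, the follow-up table of Revised Protocol 07d (Table 5.1-7) gives the rule "Only for subjects without progression on study therapy and even if they receive subsequent treatment". Sections 5.3.1 and 5.4 and the on-study tables say that, crossover subjects apart, scans are not required once subsequent therapy begins. The follow-up table of Revised Protocol 08 (Table 5.1-6) says the same.

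On the quantity measured, Sections 5.4.1 and 8.3.1 speak of tumour volume and Section 8.4.2.1 of tumour burden. Appendix 3, Section 2.1, states: "The baseline sum diameters will be used as reference to further characterize any objective tumor regression in the measurable dimension of the disease".

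**The concern.** Depth of response is meant to describe the responses that make up ORR, but it is read from a wider set of scans. Consider a subject who stops for toxicity without progression, starts another anti-cancer treatment and is scanned again. BOR ignores the later scans. As 8.3.1 is written, the nadir does not. Shrinkage caused by the next treatment can then appear in the study-drug summary, and the error can only make depth look greater.

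The naming adds a second difficulty. A percent decrease in volume, in a sum of diameters and in an undefined burden are different numbers for the same lesions, and 8.3.1 names the one that the trial does not measure.

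**Working it through.** **Windows side by side**

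| Measure | Closes or is censored at | Cut at new therapy? |
|---|---|---|
| BOR/ORR (8.3.1, 5.4.2) | progression or subsequent therapy | yes |
| PFS (8.3.2) | progression or death; censored before new therapy | yes |
| DOR (8.3.1) | progression or death; PFS censoring rule if neither occurs | by reference |
| Depth of response (8.3.1) | progression or death | no |

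Depth of response is the only one of the four without the cut.

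**Can scans after new therapy exist?** Under Table 5.1-7 of Revised Protocol 07d they are scheduled for non-progressed subjects. Section 3.1.12 also continues scans after a stop for reasons other than progression until progression, and does not mention new therapy. Under Sections 5.3.1 and 5.4 they are optional: nothing prohibits them, and nothing in 8.3.1 removes them from the nadir. So the route is open, but its width depends on which imaging passage sites follow.

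**Illustration (assumed values).** A subject has a best on-study change of −10%, stops without progression, starts another therapy and reaches −40%, still without progression. BOR remains stable disease, because the later scans fall outside its window. Depth under 8.3.1 is 40%, beyond the 30% threshold for partial response. The gap is 40 − 10 = 30 points. Section 8.4.2.1 places the efficacy analyses in all treated subjects, so this subject would be in the summary.

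**Size across a cohort (assumption only).** If a share q of the subjects summarised has a later nadir deeper by e points, the mean best reduction shifts by q × e.

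- q = 5%, e = 10: 0.05 × 10 = 0.5 points
- q = 10%, e = 20: 0.10 × 20 = 2 points
- q = 20%, e = 30: 0.20 × 30 = 6 points

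The protocol gives neither q nor e, so 0.5 to 6 points shows only how the result scales. It is not an estimate.

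**Scale.** Appendix 3 (Section 3.2.1.2) equates a 20% increase in diameter with a 73% increase in volume. Cubic scaling reproduces this: 1.2³ − 1 = 0.728. On the same scaling, the 30% diameter decrease that defines partial response is 1 − 0.7³ = 1 − 0.343 = 0.657, or 66% by volume. The protocol's own conversion therefore shows that the two terms are not interchangeable. Appendix 3 records target lesions as diameters, and Section 5.4.4 is unidimensional; no volumetric measurement is specified anywhere.

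**The case against.** The strongest reply is that the protocol has largely closed the route. Clarifying that scans are not required after subsequent therapy was a stated purpose of Revised Protocol 07d, and Sections 5.3.1 and 5.4 and the on-study tables carry that text. Revised Protocol 08 has it in the follow-up table too. The cell in Table 5.1-7 looks like a leftover. This stands as far as it goes: one should say that later shrinkage *can be* credited, not that it *is*. It does not remove the point, because the 8.3.1 window is unchanged in both versions and scans that are merely not required can still be done and counted.

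Second, the measure is descriptive under 8.4.2.1, with no test, threshold or sample size attached. This stands in full.

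Third, volume is probably loose wording. Only diameters are collected, and Appendix 3 already names the baseline sum of diameters as the reference for regression, so no volume percentage could be produced from the planned data. This also stands: the naming limb is a terminology error.

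A reader might go further and tie the matter to Section 3.1.2.1, where one criterion is "A majority of subjects who discontinue due to treatment related AEs have deep tumor response", set at more than 80% reduction without a unit. That criterion triggers a risk/benefit discussion in dose escalation. It is not the 8.3.1 endpoint and adds no weight here.

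A reader might also infer that the combination arms are most affected, from the 10 of 53 combination subjects (18.9%) in the cited melanoma study who stopped for related adverse events. That figure does not count subjects who were progression-free, started new therapy, were rescanned and reached a deeper nadir. Section 4.5.5 also lets some subjects with ipilimumab-only toxicity continue nivolumab. The documents support no statement about differences between arms.

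**Conclusion.** The point holds in a limited form. The 8.3.1 definition leaves out a cut that BOR has and that PFS censoring applies, and under Table 5.1-7 of Revised Protocol 07d the resulting scans are scheduled. Depth of response can therefore include shrinkage produced by a later treatment. The direction is upward, since a longer window can only keep or deepen a nadir. The size cannot be computed from the protocol.

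A reader might infer that the primary result is biased. It is not: BOR is cut at subsequent therapy, so ORR and its powers do not change, and neither do DOR or PFS.

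The conclusion rests on reading 8.3.1 as written. The protocol itself fixes the window there, so this is not a detail left open for the SAP.

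**What to change.** In Section 8.3.1 of both protocol versions, define depth of response as the best percent change from baseline in the RECIST 1.1 sum of target-lesion diameters, using assessments up to the first of documented progression, start of subsequent anti-cancer therapy, or death. Use that one term in 5.4.1, 8.3.1 and 8.4.2.1 in place of tumour volume and tumour burden.

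Separately, reconcile Table 5.1-7 of Revised Protocol 07d with Sections 5.3.1 and 5.4 on scans after subsequent therapy. The revised definition gives the same window whichever imaging rule is kept.

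The cost is wording only. No new data are needed, and the start of subsequent therapy is already required for BOR and PFS. Some subjects' best reduction will be slightly less favourable.

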8.3.2 Secondary Endpoint(s)

The secondary objective (to assess the safety and tolerability of nivolumab monotherapy, nivolumab combined with ipilimumab in subjects with advanced or metastatic tumors, or nivolumab combined with ipilimumab and cobimetinib in subjects from the additional pancreatic cancer cohort only) will be primarily assessed by the rate of treatment-related AEs leading to drug discontinuations during the first 12 weeks of treatment. In addition, safety and tolerability will be analyzed through the incidence of adverse events, serious adverse events, and specific laboratory abnormalities (worst grade) in each cohort. Toxicities will be graded using the National Cancer Institute (NCI) Common Terminology Criteria for Adverse Events (CTCAE) version 4.0.

PFS is defined as the time from treatment assignment in IVRS to the date of the first documented tumor progression, as determined by the investigator or BICR for selected tumor types (per RECIST 1.1), or death due to any cause, whichever occurs first. Subjects who die without a reported prior progression will be considered to have progressed on the date of their death. Subjects who did not progress or die will be censored on the date of their last evaluable tumor assessment. Subjects who did not have any on-study tumor assessments and did not die will be censored on the date they were assigned treatment in the IVRS. Subjects who started anti-cancer therapy either prior to death or without a prior reported progression will be censored on the date of their last evaluable tumor assessment prior to the initiation of subsequent anti-cancer therapy.

OS is defined as the time between the date of treatment assignment in IVRS and the date of death due to any cause. A subject who has not died will be censored at the last known alive date. OS will be followed continuously while subjects are on the study drug and every 3 months via in-person or phone contact after subjects discontinue the study drug.

[REDACTED]

[REDACTED]

[REDACTED]

[REDACTED]

[REDACTED]

index.

8.4 Analyses

8.4.1 Demographics and Baseline Characteristics

Demographic and baseline characteristics will be summarized in all treated subjects by cohort, as randomized or assigned, using descriptive statistics.

8.4.2 Efficacy Analyses

8.4.2.1 Primary Endpoint Methods

The efficacy analyses will be performed on the all treated population. ORR will be summarized for each cohort by a binomial response rate and corresponding two-sided 95% exact CI using the method proposed by Atkinson and Brown⁹⁶ for cohorts using two-stage design and the Clopper-Pearson method for cohorts using the one stage design⁹⁷.

For SCLC expansion cohort, the estimated difference along with its corresponding p-value of ORR assessed by BICR between nivolumab monotherapy and nivolumab/ipilimumab combination therapy (nivolumab 1 mg/kg + ipilimumab 3 mg/kg) will also be presented with 95% CI. Similar methods will be used to summarize ORR for each stratification factor. However the p-value will not be provided for each stratification factor.

DOR as determined by the investigator or BICR for selected tumor types will be summarized for subjects who achieve confirmed PR or CR using the Kaplan-Meier (KM) product-limit method. The median value, along with two-sided 95% CI using the Brookmeyer and Crowley method,

will also be calculated by cohort. In addition, the percentage of responders still in response at different time points (3, 6, and 12 months) will be presented based on the KM plot.

The magnitude of reduction in tumor burden will be summarized descriptively. Immune related responses will be summarized descriptively.

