1.3 Objectives(s)

1.3.1 Primary Objective

SCLC Expansion Cohort

- To compare the objective response rate (ORR) as assessed by a Blinded Independent Central Review (BICR) for nivolumab monotherapy versus nivolumab combined with ipilimumab (nivolumab 1 mg/kg + ipilimumab 3 mg/kg).

Other Cohorts

- To evaluate the objective response rate (ORR) of nivolumab monotherapy, nivolumab combined with ipilimumab in subjects with advanced or metastatic tumors, or nivolumab combined with ipilimumab and cobimetinib in subjects from the additional pancreatic cancer cohort only. ORR will be assessed by the BICR in selected tumor types.

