5.4.1 Primary Efficacy Assessment

The primary endpoint is objective response rate (ORR) in all assigned subjects as determined by the investigators. ORR is defined as the number of subjects with a best overall response (BOR) of complete response (CR) or partial response (PR) divided by the number of assigned subjects. The investigator-determined ORR will be further characterized by the investigator-determined duration of response (DOR) and the magnitude of reduction in tumor volume. ORR and DOR will be assessed by BICR in selected tumor types.

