5.4.2 Best Overall Response

The best overall response is determined once all the data for the subject is known. It is defined as the best response designation, as determined by the investigator or BICR for selected tumor types, recorded between the date of first treatment and the date of objectively documented progression per RECIST1.1 or the date of subsequent therapy, whichever occurs first. For subjects without documented progression or subsequent therapy, all available response designations will contribute to the BOR assessment. The subject's best overall response assignment will depend on the findings of both target and non-target disease and will also take into consideration the appearance of new lesions.

Complete or partial responses may be claimed only if the criteria for each are met at a subsequent time point (minimum 4 weeks after criteria of objective response are first met). In this circumstance, the best overall response can be interpreted as in Table 5.4.2-1.

Table 5.4.2-1: Best overall response when confirmation of CR and PR required

Overall Response First Timepoint	Overall Response Subsequent Timepoint	Best Overall response
CR	CR	CR
CR	PR	SD, PD or PR ^a
CR	SD	SD provided minimum criteria for SD duration met, otherwise, PD
CR	PD	SD provided minimum criteria for SD duration met, otherwise, PD
CR	NE	SD provided minimum criteria for SD duration met,

Table 5.4.2-1: Best overall response when confirmation of CR and PR required

Overall Response First Timepoint	Overall Response Subsequent Timepoint	Best Overall response
		otherwise NE
PR	CR	PR
PR	PR	PR
PR	SD	SD
PR	PD	SD provided minimum criteria for SD duration met, otherwise, PD
PR	NE	SD provided minimum criteria for SD duration met, otherwise NE
NE	NE	NE

CR = complete response, PR = partial response, SD = stable disease, PD = progressive disease, and NE = inevaluable.

^a If a CR is truly met at first time point, then any disease seen at a subsequent time point, even disease meeting PR criteria relative to baseline, makes the disease PD at that point (since disease must have reappeared after CR). Best response would depend on whether minimum duration for SD was met. However, sometimes ‘CR’ may be claimed when subsequent scans suggest small lesions were likely still present and in fact the patient had PR, not CR at the first time point. Under these circumstances, the original CR should be changed to PR and the best response is PR.

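### Primary ORR is defined over assigned subjects in Section 5.4.1 but over treated subjects in Section 8, so the one formally tested randomised comparison (SCLC expansion) rests on a post-randomisation subset

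*Protocol*

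**What the plan says.** - Section 5.4.1 (Primary Efficacy Assessment): "The primary endpoint is objective response rate (ORR) in all assigned subjects as determined by the investigators". The count of responders is "divided by the number of assigned subjects". The section ends by noting that BICR will be used in selected tumour types, which it does not name.
- Section 8.3.1 (Primary Endpoint): the same count is "divided by the number of treated subjects".
- Section 8.4.2.1 (Primary Endpoint Methods): "The efficacy analyses will be performed on the all treated population". The next paragraph sets out the SCLC expansion difference in BICR-assessed ORR, its p-value and its 95% CI, with no other population named.
- Section 8.2: "All Treated Subjects: All subjects who received at least one dose of any study medication". The assigned set is defined through the dose escalation phase ("All Assigned Subjects: All subjects who were assigned to the highest tested tolerated dose level in the Dose Escalating Safety Evaluation Phase") and the staged enrollment phase. It does not mention the SCLC expansion.
- Section 8.1: 150 versus 100 subjects, randomised 3:2 and stratified by prior lines, two-sided 5% type I error, 78% power for 10% versus 23%.
- Section 6.1.1 requires SAE collection for 30 days in subjects randomised but never treated.

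The file holds two protocol revisions (07D and 08). Both carry this conflict.

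**The concern.** A primary endpoint should have one denominator. Here the assessment section and the statistical section give different ones.

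For cohorts without a between-arm test, a treated denominator is a common and reasonable choice. The SCLC expansion is different because its comparison relies on randomisation. The study is open label, so the arm is known between assignment and first dose. Restricting the analysis to dosed subjects conditions on something that happens after randomisation. Untreated subjects have no response, so leaving them out raises the observed ORR of whichever arm loses more of them. At stake is the validity of the only p-value in the plan. BICR limits reading bias but cannot bring excluded subjects back.

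**Working it through.** **1. The plan's own figure.** Inputs from Section 8.1: N = 150 and 100, ORR 10% and 23%, two-sided 5%.

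- Pooled rate = (150 × 0.10 + 100 × 0.23)/250 = 38/250 = 0.152
- SE under the null = √[0.152 × 0.848 × (1/150 + 1/100)] = 0.04635
- SE under the alternative = √[0.10 × 0.90/150 + 0.23 × 0.77/100] = 0.04869
- Power = Φ[(0.13 − 1.96 × 0.04635)/0.04869] = Φ(0.804) = 78.9%

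The stated 78% is reproduced, so the sample size is not in question.

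**2. Type I error of a treated-only test.** The protocol gives no untreated share, so the shares u₁ (monotherapy) and u₂ (combination) are assumptions. Let ORR over all randomised subjects be 15% in both arms and let untreated subjects be non-responders. The treated-only analysis then has nᵢ = Nᵢ(1 − uᵢ) and response rate 0.15/(1 − uᵢ). Binomial probabilities are summed over all outcomes (x, y) with |z| > 1.96, where z = (y/n₂ − x/n₁)/√[p̄(1 − p̄)(1/n₁ + 1/n₂)] and p̄ = (x + y)/(n₁ + n₂).

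| Untreated, mono / combination | Treated n | Treated-only ORR | Two-sided error | Favouring combination |
|---|---|---|---|---|
| 0% / 0% | 150 / 100 | 15.0% / 15.0% | 5.1% | 2.6% |
| 2% / 2% | 147 / 98 | 15.3% / 15.3% | 5.1% | 2.6% |
| 2% / 8% | 147 / 92 | 15.3% / 16.3% | 5.5% | 4.2% |
| 0% / 10% | 150 / 90 | 15.0% / 16.7% | 6.7% | 5.7% |
| 10% / 0% | 135 / 100 | 16.7% / 15.0% | 6.1% | 1.0% |

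The last row shows the direction reversing when the imbalance lies in the monotherapy arm. At an equal ORR of 10%, false findings favouring the combination are 2.5% with none untreated, 3.7% at 0%/5% and 5.0% at 0%/10%.

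**3. A single data set, with assumed counts.** 15/150 versus 18/100 in all randomised subjects is a difference of 8.0 points, chi-square p = 0.067. If 2 and 8 subjects were never dosed, 15/148 versus 18/92 is 9.4 points, chi-square p = 0.039. With 3 and 2 undosed (2% per arm), 15/147 versus 18/98 gives p = 0.067, unchanged.

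**4. Power if all randomised subjects are analysed.** Each rate is multiplied by (1 − uᵢ), with N kept at 150 and 100. At 2%/2% the rates are 9.8% and 22.5%, and power is 78.0%. It is 76.5% at 5%/5%, 72.6% at 0%/5% and 65.2% at 0%/10%.

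**The case against.** The strongest reply is that Section 8 is consistent with itself, since 8.3.1 and 8.4.2.1 both say treated, and Section 3.1.4 describes the arms as 150 and 100 subjects treated. On this view Section 5.4.1 is leftover general wording. First dose is due within 3 days of assignment (Section 3.1.12; 3 working days in Section 4.4), so few subjects may go undosed. This stands as a limit on size. It does not remove the contradiction, and it does not justify a treated-only population for a randomised test.

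Several stronger readings are tempting, but the documents do not support them:

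- **The assessor is open for the SCLC comparison.** It is not. Sections 1.3.1, 3.1.4, 8.3.1 and 8.4.2.1 all fix BICR. Only the general sentence in 5.4.1 names investigators.
- **The best-response window changes the result.** Section 5.4.2 counts responses "recorded between the date of first treatment and the date of objectively documented progression", whereas 8.3.1 starts at randomisation or assignment. With dosing due within days and the first scan at 6 weeks from first dose, ORR is the same either way.
- **The combination's toxicity shows which way the bias runs.** Toxicity cannot occur before the first dose. Monotherapy subjects in this cohort have no crossover option and could equally decline to start.
- **The p-value example shows that the conclusion flips.** The protocol names no test. For 15/148 versus 18/92, Fisher's exact test gives 0.053 and the continuity-corrected chi-square 0.062, so neither crosses 5%.

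**Conclusion.** The denominator contradiction is real and holds even if every subject is dosed. Section 8.4.2.1 also fixes the only formally tested randomised comparison on a subset formed after randomisation, in a protocol that foresees randomised but untreated subjects.

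A reader might infer that the comparison is demonstrably biased towards the combination. That is not established, because the protocol gives neither the number nor the arm of untreated subjects. Bias is zero if all are treated, and type I error is essentially unchanged if non-starting is low and balanced. The 6.7% figure needs the extreme assumption of 0% versus 10% untreated. All the error rates assume untreated subjects are non-responders and an uncorrected chi-square. The case for change is that the risk is avoidable and cheap to remove, not that a particular bias has been shown.

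Other arms are randomised too (ovarian 1:1:1, for example) but have no stated between-arm test, so the point is confined to the SCLC expansion.

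**What to change.** - **Sections 8.3.1 and 8.4.2.1:** for the SCLC expansion, make the primary analysis BICR-confirmed ORR in all randomised subjects, as randomised, counting untreated or unevaluable subjects as non-responders. Keep all treated as a sensitivity analysis. Keep treated subjects as the denominator for cohorts without a between-arm test.
- **Section 8.2:** name the all-randomised set for the expansion, since the assigned definition does not mention it.
- **Section 5.4.1:** match the denominators above and state BICR for the SCLC expansion.
- **Section 5.4.2:** align the best-response start date with 8.3.1, as a wording change only.

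Apply the same text to both protocol revisions. Whether the test is stratified by prior lines is a separate matter that the SAP can hold.

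The cost is wording and one extra table. No new data are needed, because Section 5.9 already plans BICR for randomised subjects. Reported ORR may be slightly lower. Power falls slightly if few subjects are untreated (78.0% at 2% in both arms, against 78.9% with none). It falls further only if non-starting is more frequent or lopsided, and in that case the treated-only result would also be least trustworthy.
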